# **Nutrition ameliorates the muscle loss of pre-sarcopenia in elderly**

## **1. Background and Research Objectives**

Population aging has become a global concern. Taiwan is projected to enter a “super-aged society” by 2025, with individuals aged 65 and above comprising over 20% of the total population (approximately 4.81 million people). Older adults often suffer from degenerative diseases, leading to progressive disability and diminished quality of life and dignity. Among the physiological declines associated with aging, loss of muscle mass is particularly prominent. When accompanied by reduced muscle strength or physical function, this condition is defined as sarcopenia. Sarcopenia has recently been recognized as a geriatric syndrome and is associated with adverse clinical outcomes such as disability, falls, injuries, hospitalization, and poor recovery from illness. It is considered a major contributor to loss of independence in older adults. Currently, there is no definitive clinical biomarker for sarcopenia. Functional assessments often reflect fatigue and frailty but do not necessarily indicate sarcopenia itself.

This subproject will recruit participants from the main integrated aging study and identify individuals with **pre-sarcopenia** for nutritional intervention. We plan to collect blood and urine samples from 120 participants at two time points: mid-intervention (6 weeks) and post-intervention (12 weeks). Functional assessments related to sarcopenia will be conducted after the intervention. Using metabolomics approaches, we aim to evaluate the effectiveness of nutritional supplementation, identify potential biomarkers for risk sarcopenia, and assess their prognostic value. The findings will contribute to understanding the physiological mechanisms of sarcopenia and support future therapeutic monitoring.

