#### **2.5 Sample Size: 120 participants**

#### **2.6 Measurements, Duration, and Risks Study Procedures:**

- 2.6.1 Participants will undergo nutritional assessment via questionnaire and receive a daily supplement containing 8.5 g whey protein and 1.5 g leucine for 12 weeks.
- 2.6.2 At week 6, participants will return for blood (5 mL) and urine (10 mL) collection and report supplement adherence.
- 2.6.3 At week 12, participants will return for a second round of blood and urine collection, supplement adherence assessment, and sarcopenia-related functional tests (body composition, grip strength, walking speed, and calf circumference).

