#### **2.8 Nutritional supplementation**

Participants received sachets containing the nutritional supplement and were instructed to consume two sachets daily over a 12-week intervention period. Each 8 g serving provided 35 kcal, comprising 4.1 g of protein, 1 g of fat, and 2.4 g of carbohydrates. Follow-up assessments were conducted throughout the intervention to monitor adherence. Participants were asked to return both used and unused sachets at each visit, and compliance was defined as consumption of at least 80% of the provided sachets.

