## **2.10 Statistical Analysis**

Metabolomic data will be processed using Topspin and MassLynx for spectral alignment and peak extraction, followed by multivariate analysis with SIMCA-P, including principal component analysis (PCA). Univariate statistical comparisons will be conducted using t-tests and ANOVA for group-level differences. Paired t-tests will be applied to assess within-subject changes before and after nutritional supplementation. Changes in metabolite concentrations in plasma and urine will be linked to individual health indicators to identify biomarkers associated with healthy aging.

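### The only stated biomarker rule uses metabolite changes in people who all take whey and leucine, so supplement intake or response markers can be reported as risk or healthy-aging markers

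*Combined protocol and SAP*

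**What the plan says.** Section 1 sets several aims. One is to evaluate the supplement. Another is to "identify potential biomarkers for risk sarcopenia, and assess their prognostic value".

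Section 2.6.1 has participants "receive a daily supplement containing 8.5 g whey protein and 1.5 g leucine for 12 weeks". No control, placebo or unsupplemented group is described anywhere.

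Section 2.10 contains one sentence on finding biomarkers: "Changes in metabolite concentrations in plasma and urine will be linked to individual health indicators to identify biomarkers associated with healthy aging". It names no model and no covariate, and it does not define the health indicators. The same section plans PCA and two kinds of univariate test:

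- "Univariate statistical comparisons will be conducted using t-tests and ANOVA for group-level differences", with the groups left undefined.
- "Paired t-tests will be applied to assess within-subject changes before and after nutritional supplementation".

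Adherence is assessed at weeks 6 and 12 (Sections 2.6.2 and 2.6.3). Section 2.8 has sachets returned at each visit, and "compliance was defined as consumption of at least 80% of the provided sachets". Section 2.10 uses neither the sachet data nor the threshold.

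The sampling times disagree. Sections 1 and 2.6 place blood and urine collection at weeks 6 and 12 only, and Section 2.7.1 counts two blood draws. Section 2.9 reports fasting samples before and after supplementation, and the paired test in Section 2.10 presupposes that pair.

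**The concern.** A marker of sarcopenia risk should say something about older people who are not taking the supplement. The only rule given for finding biomarkers uses metabolite change across, or within, a period when everyone described is taking it. Leucine, other whey amino acids and their breakdown products can change because they are being consumed, whatever happens to muscle. The plan has no step that separates a metabolite responding to the supplement from one that reflects muscle risk.

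There is also a possible route to a false link between people. If those who take more sachets also function better, adherence alone will connect metabolite change to function. Controlling the false discovery rate would not remove this, because the correlation would be real but due to intake.

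At stake is the meaning of the biomarker list. A metabolite that tracks intake or response could be put forward as a marker of risk or healthy aging.

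**Working it through.** **Plan's own figure.** The only number available is "2.5 Sample Size: 120 participants". It comes with no significance level, power, effect size, standard deviation or dropout allowance, so it cannot be reproduced. The point does not depend on it; n = 120 is used below for illustration and assumes that everyone completes.

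**Aim against analysis.**

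| Element | What the documents give |
|---|---|
| Target | Sarcopenia risk and prognostic value (Section 1) |
| Biomarker input | Metabolite change linked to health indicators (Section 2.10) |
| Supplement exposure | All participants described (Section 2.6.1) |
| Unsupplemented comparison | None described |
| Role of adherence in the analysis | None stated |
| Pre-supplement sample | Reported in 2.9 and presupposed in 2.10; absent from 1, 2.6 and 2.7 |

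The mismatch between a risk aim and change under supplementation can be read from this table without any assumed number.

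**What a uniform supplement effect does.** If everyone's level shifts by the same amount, a paired t-test will find the shift. Approximate power is Φ(d√120 − 1.96), with d the mean shift in SD units (assumed): 0.59 at d = 0.2, 0.91 at d = 0.3, and above 0.99 at d = 0.5. Such a shift creates no correlation between people with function.

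**When a false between-person link arises.** Let a be the correlation of adherence with metabolite change, and b its correlation with a functional indicator, with nothing else connecting the two. Then:

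- Induced correlation: r = a × b.
- Standard error of Fisher z: 1/√(120 − 3) = 1/√117 = 0.0925.
- Two-sided 0.05 (assumed): |r| above about tanh(1.96 × 0.0925) = 0.18 is declared significant.
- Probability of declaration: Φ(m − 1.96) + Φ(−m − 1.96), where m = atanh(r) × √117.

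The documents give no value for a or b; all pairs below are assumptions.

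| a | b | r | m | Declared associated |
|---|---|---|---|---|
| 0.5 | 0 | 0 | 0 | 5% |
| 0.3 | 0.1 | 0.03 | 0.32 | about 6% |
| 0.2 | 0.2 | 0.04 | 0.43 | about 7% |
| 0.3 | 0.3 | 0.09 | 0.98 | 16% |
| 0.4 | 0.4 | 0.16 | 1.75 | 42% |
| 0.5 | 0.4 | 0.20 | 2.19 | 59% |

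A simulation with 5,000 runs per scenario agreed where the pairs overlap: 0.044 at 0.5/0, 0.159 at 0.3/0.3 and 0.600 at 0.5/0.4.

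**Effect of adjusting.** In the same simulation, using adherence as a covariate (partial correlation) gave rates of 0.046 to 0.057 in every scenario. That simulation assumes adherence is measured without error and has no real effect on function.

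**The case against.** Several objections have force.

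- **Universal supplementation does not by itself produce false links.** A reader might infer that it does. The working shows otherwise: adherence must vary and must correlate with function, and nothing in the documents shows the second. This stands, and it makes the larger rates conditional rather than expected.
- **Section 2.10 is not confined to change scores.** A reader might infer that no analysis of metabolite levels is possible under the plan. PCA and the tests of undefined groups do not exclude one. The supported criticism is narrower: the only sentence saying how biomarkers will be identified uses change, and no baseline-level analysis is stated.
- **Change is the right material for some aims.** Section 1 also wants to evaluate the supplement and support therapeutic monitoring. This stands; the fault is only that response markers are not kept apart from risk markers.
- **Adjustment for adherence can do harm.** If intake improves muscle, adherence lies on the path to a genuine response, and adjusting may remove dose-response signal. This stands, so the adjusted model should not be the sole analysis.
- **Fasting samples and cautious wording.** Overnight fasting (Section 2.9) reduces the immediate post-dose signal but does not rule out effects of 12 weeks of intake. The aim is worded cautiously, as a search for possible markers and associations, but that does not separate the two kinds of marker.
- **A pre-supplement sample may not exist.** A reader might infer from Section 2.9 that one is certainly available. Sections 1, 2.6 and 2.7 contradict that, so any remedy using it must be conditional.

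**Conclusion.** The concern holds in a limited form. As written, the plan lets markers of supplement intake or response be reported as markers of healthy aging or sarcopenia risk, because its one biomarker rule uses change under supplementation, has no unsupplemented comparison and ignores the adherence data. This follows from the text alone.

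The size of any false between-person association is not known. It runs from the nominal 5% when adherence is unrelated to function, through about 7% (0.2/0.2) and 16% (0.3/0.3), to 59% (0.5/0.4). These figures rest on assumed correlations, 120 completers and two-sided 0.05. They show what could happen, not what is expected.

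If samples were taken only at weeks 6 and 12, the problem is worse: no supplement-free metabolite measurement exists, and the risk-marker aim cannot be met for unsupplemented people.

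**What to change.** 1. Reconcile Sections 1, 2.6 and 2.7 (draws at weeks 6 and 12 only) with Sections 2.9 and 2.10 (before and after supplementation).
2. If a pre-supplement sample exists, relate its metabolite levels to baseline muscle mass, grip strength and walking speed, the eligibility measures in Section 2.3.5. Confirm that all three were recorded for each participant, since eligibility requires only one. Report the results as cross-sectional candidate markers in a sample selected on those measures, not as prognostic markers. If no such sample exists, state that unsupplemented risk markers cannot be identified.
3. Report metabolite change against function as supplement-response markers, with and without the returned-sachet fraction as a covariate. Note that sachet counts are imperfect, that adjustment may remove genuine dose-response signal, and that it does not replace a control group.
4. State that no metabolite identified from change alone will be called a biomarker of sarcopenia risk or healthy aging.

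The cost is a revision of Section 2.10, a baseline-level analysis if the sample exists, and one extra sensitivity model using sachet returns already planned. The downside is a shorter list of claimed biomarkers and, if there is no pre-supplement sample, giving up the risk-marker claim for unsupplemented people.
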